6.3 Follow-up of adverse events

All AEs will be followed until they have abated, or until a stable situation has been reached. Depending on the event, follow up may require additional tests or medical procedures as indicated, and/or referral to the general practitioner or a medical specialist. SAEs need to be reported till end of study within the Netherlands, as defined in the protocol.

6.4 [Data Safety Monitoring Board (DSMB) / Safety Committee]

Given the low-risk character of the study, no Data Safety Monitoring Board is installed or interim analyses are planned.

7. STATISTICAL ANALYSIS

All measured data will be assembled in a computer database and analysed using SPSS 25.

7.1 Primary study parameters

As mentioned in chapter 6.1.1, the QRISK3 score is calculated based on several parameters that are collected during regular cardiovascular risk management consultations as part of usual care. For age, we will use age at baseline (T0) at all measurement points. Since the QRISK3 score cannot be calculated when individual items are missing, we will use the following values:

- In case ethnicity is missing, we will use “white or not stated”.

- In case smoking status is missing, we will use “non-smoker”.
- In case the patient is a smoker, but the amount of cigarettes is not stated, we will use “moderate (10-19)”.
- In case cholesterol/HDL ratio is missing, we will use 4.4 for men and 3.7 for women (11). In case systolic blood pressure is missing, we will use the latest measurement of this value, or, if no measurements are available, we will use 129mmHg for men and 123mmHg for women (11).
- In case standard deviation of systolic blood pressure is missing, we will use “0”.
- In case either weight or both length and weight are missing, we will use the latest measurement of the Body Mass Index, or, if no BMI is available, we will use Body Mass Index values as mentioned in table 2.
- In case only length is missing at all measurement points, we will use values as mentioned in appendix ... for calculating Body Mass Index.
- In case calculated Body Mass Index is $<20\text{kg/m}^2$, the value is set to 20kg/m^2 , as the algorithm is not validated for values of Body Mass Index lower than 20kg/m^2 .

Age (years)	Men	Women
25-39	25.2	24.4
40-49	26.2	24.7
50-59	26.5	25.7
60-84	26.8	26.4

Table 2. Mean Body Mass Index (kg/m^2) by age and gender, based on RIVM 2012.

- In case family history of premature coronary heart disease in a first degree relative is “yes” at any measurement point, all measurement points will be set to “yes”, as this factor might not be manifest at the start of enrolment, but does contribute to the patient’s cardiovascular risk, regardless to the moment this factor becomes manifest. This also applies for the factors migraines, rheumatoid arthritis, systemic lupus erythematosus, and erectile dysfunction.
- In case a patient starts blood pressure treatment due to the intervention, all prior measurement points will be set to “yes”, as the indication for blood pressure treatment would have been present provided the patient was on appropriate usual care.

The MHI-5 consists of five questions with each six answer categories: continuously-mostly-often-sometimes-rarely-never. The answers of the positively formulated questions (questions 3 and 5) will be assigned the values 5, 4, 3, 2, 1, and 0, respectively. The

answers of the negatively formulated questions (questions 1, 2, and 4) will be assigned the values 0, 1, 2, 3, 4, and 5, respectively. Subsequently, a sum score will be calculated, multiplied by 4, resulting in an MHI-5 score ranging from 0 to 100, where a score of 100 equals perfect mental health.

Data analysis will be performed according to the intention-to-treat principle. Data from patients who discontinued follow-up will be included in the analysis up to the point of dropout. Descriptive analyses will be performed to describe the patient characteristics. Mean and standard deviation (std) or median and interquartile range for continuous characteristics and number and percentages for categorical characteristics will be determined. The relationship between treatment and outcome measures measured at 5, 10, 15, and 20 month follow up will be analysed with mixed three level linear or logistic regression, taking into account that the times of measurement are clustered within patients, and patients within general practices. We will perform a model with a random intercept and all other variables fixed. To test the effect of the intervention a model with time, group (intervention or control) and the interaction between time and group will be performed. A value of $p < 0.05$ will be considered statistically significant for all analyses, based on two-sided testing. Analyses will be performed using the Statistical Package for Social Sciences (SPSS, IBM Corp., Armonk, NY) version 25.

We will present QRISK3 scores and MHI-5 scores as means (SDs) for every measurement point, with notification of the number of patients included in the calculation.

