The potential benefit of participation is high, as changes in antipsychotic medication and appropriate cardiovascular risk screening and management will result in decreased cardiovascular risk.

Burden and risk associated with outcomes measurements:

Patients fill in questionnaires at baseline and every 5 months during follow-up. Based on our experiences in the pilot study, we expect that it will take approximately 20 minutes to fill in

the questionnaire. For the assessment of the primary outcome QRISK3 score routinely collected data from the cardiovascular risk management programme, i.e. blood pressure, body weight, smoking behaviour, and blood cholesterol and glucose levels.

INTRODUCTION AND RATIONALE

Antipsychotic medication is effective for a variety of psychiatric disorders, such as schizophrenia, bipolar disorder, schizoaffective disorder, or major depressive disorder. Remarkably, however, a large proportion of patients on antipsychotics do not have a diagnosis of a severe mental illness (6). Jakobs et al. found that, among patients in general practices who use antipsychotic medication, up to 68% did not have a registered diagnosis of a severe mental illness. These patients are using antipsychotics off-label. Reasons for off-label prescription can be anxiety, dementia, or sleep- and personality disorders.

The use of antipsychotic medication is increasing worldwide (1-3), but this is not without risk. It is well established that patients with a severe mental illness and patients treated with antipsychotics have excess metabolic dysfunction (4) and are at an increased risk of cardiovascular disease (4, 5). The increased risk of cardiovascular disease is multifactorial. Patients with a severe mental illness or on antipsychotic medication tend to have a high incidence of lifestyle risk factors, such as poor diet, lack of exercise, stress and smoking, besides possible genetic susceptibility (8, 9). Furthermore, there is evidence that people with severe mental illness are less likely to receive standard levels of care (5). Moreover, antipsychotics can cause weight gain, hypertension, glucose intolerance and dyslipidaemia, and can cause cardiac toxicity (10).

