on antipsychotic use, and the QRISK3 score at baseline (see Methods 6.1.2. Secondary study parameters).

During the multidisciplinary meeting, the participating patient (and carer), the general practitioner, a psychiatrist, the primary care nurse, and if desired an experience expert (patient coach who lived the experience) will review the patient's antipsychotic use and all other relevant medication (if applicable). Also, possible cardiovascular risk factors will be addressed, such as smoking status, blood pressure, Body Mass Index, blood glucose and cholesterol levels. The multidisciplinary meeting will result in a set of individualised treatment suggestions, including advice on antipsychotic use (e.g. continuation, deprescribing, or switching) and reducing cardiovascular risk.

Step 3: A week after the multidisciplinary meeting, the patient has a consultation with the general practitioner during which the set of individualised treatment suggestions will be translated into an action plan through shared-decision making. This shared-decision making process will benefit the adherence and outcome of the plan. The plan will also define the tasks and responsibilities of the various healthcare providers. Potential actions are altering antipsychotic use, initiating antihypertensive medication or statins, referral to the chronic care nurse (in Dutch: POH-S) for example for smoking cessation, referral to the primary care mental health nurse (in Dutch: POH-GGZ), the dietician, the physical therapist, or a life style coach.

The effects of TACTIC in addition to usual care will be compared to usual care alone, in which patients will be their own comparator, prior to treatment initiation.

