After signed informed consent and inclusion, baseline measurement will take place and patients will fill in a digital questionnaire using Castor EDC, containing MHI-5, EQ-5D-5L, TIC-P and LUNSERS. As part of the preparation for the multidisciplinary meeting, patients will be asked to fill in a custom-made questionnaire on antipsychotic use. This questionnaire will help healthcare professionals prepare for the meeting and will give the patient insight in possible topics that can be addressed during the meeting. In case patients do not have an email address, we will send the questionnaires by mail. Patients will then watch the information video at home, attend the multidisciplinary meeting, and attend a consultation with their general practitioner, as described in section 5. At five months follow-up, patients will be invited for follow-up (monitoring) measurements at the general practice as part of the regular regional cardiovascular risk management programme (usual care), to undergo physical examination (measuring weight and blood pressure), venapuncture and urinalysis (for measuring risk factors, i.e. HbA1c, blood glucose, lipid spectrum and kidney function). As part of the evaluation, patients will also fill in questionnaires, containing MHI-5, EQ-5D-5L, LUNSERS, TIC-P and general questions about smoking status and family history of coronary heart disease. Depending on which step the cluster has started, patients will undergo one to four follow-up measurements, every five months. This is in line with the routine check-ups patients will have in the regular cardiovascular risk management programme. During the last follow-up measurement, they are also asked to fill in the CSQ-8. Table 1 presents the schedule of assessments.

No diagnostic procedures or treatment will be postponed.

	Visit general practice	Digital information	Physical examination	Laboratory tests	Questionnaires
Week 1 Routine screening and inclusion after informed consent	X		X	X	
Week 2 Baseline measurement					X
Week 3 Information video		X			
Week 4/5	X				

Multidisciplinary meeting					
Week 5/6 Consultation with GP	X				
Month 5 Routine consultation as part of usual care. Follow-up measurement 1 Start Step 2 at Week 1	X		X	X	X
Month 10 Routine consultation as part of usual care. Follow-up measurement 2 Start Step 3 at Week 1	X		X	X	X
Month 15 Routine consultation as part of usual care. Follow-up measurement 3 Start Step 4 at Week 1	X		X	X	X

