7.3 Other study parameters

We will perform a sub analysis on the QRISK3 score, determining the proportion of patients reaching 1) an absolute risk reduction of 2.5%, which we consider as clinically relevant, and 2) a proportional risk reduction of 20% of their optimal achievable reduction. To give an example: a patient has a 10-year cardiovascular risk of 20%, but after perfectly optimising all changeable risk factors, is able to reach a 10-year cardiovascular risk of 10%. When, after the intervention, the patient reaches a QRISK3 score of 17%, this means the patient reached a 3% absolute risk reduction (i.e. 20% - 17%), and a 30% proportional risk reduction (i.e. 3% / (20% - 10%)).

As mentioned in chapter 6.1.1, the Townsend Deprivation Score is not applicable to the Dutch population. We do know, however, that deprivation has impact on cardiovascular risk. Therefore, we want to perform a secondary analysis on the QRISK3 score in which we use the Dutch equivalent of deprivation ("achterstandsindex"). In the Netherlands, we use a deprivation index for patients with low social economic status, based on employment, income and percentage of non-western immigrants. This deprivation index is applicable for approximately 10% of the Dutch population.

We decided to apply the Townsend Deprivation Score at p20 (below which are the 20% most deprived of the British population) for the 10% most deprived patients in our population. By choosing p20 instead of p10, we stay on the safe side and might underestimate the effect of deprivation, but we find this more important than overestimating its impact.

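### Missing smoking status and cholesterol/HDL ratio are replaced by fixed values even when the patient's own earlier value is known, unlike blood pressure and BMI

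*Protocol*

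**What the plan says.** Section 7.1 of the Protocol explains that QRISK3 cannot be computed with an item missing and lists what to substitute. The list follows two different standards.

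- **Smoking:** "In case smoking status is missing, we will use “non-smoker".
- **Cholesterol/HDL ratio:** "In case cholesterol/HDL ratio is missing, we will use 4.4 for men and 3.7 for women".
- **Systolic blood pressure:** "In case systolic blood pressure is missing, we will use the latest measurement of this value". The reference values of 129 and 123 mmHg apply only if the patient has no measurement at all.
- **BMI:** "we will use the latest measurement of the Body Mass Index". Table 2 applies only if no BMI exists.

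Other sections bear on the point. Section 4 names "referral to the chronic care nurse (in Dutch: POH-S) for example for smoking cessation" among the possible actions after the multidisciplinary meeting. Section 5.3 lists "general questions about smoking status and family history of coronary heart disease" in the follow-up questionnaire. The Summary and section 8.4 describe the QRISK3 inputs as "routinely collected data from the cardiovascular risk management programme, i.e. blood pressure, body weight, smoking behaviour", among others. Section 7.3 adds a responder analysis based on "an absolute risk reduction of 2.5%, which we consider as clinically relevant".

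**The concern.** Blood pressure and BMI have a two-stage rule: own latest value, then a population value. Smoking and the ratio have only the second stage, so information already held on the patient is discarded.

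For smoking, the error in an individual patient can go only one way. A smoker with a blank item becomes a non-smoker and the score falls. Smoking cessation is one of the things TACTIC may bring about, so in the QRISK3 score this false quit looks like a treatment success. For the ratio, patients above 4.4 (men) or 3.7 (women) are pulled down and those below are pulled up, so the net direction is unknown.

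At stake are a primary outcome, the responder proportion in section 7.3 and, if missingness differs between conditions, the treatment contrast itself.

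**Working it through.** **1. Is the rule really unconditional?** The bullet on length is limited to patients whose length is missing at every measurement point, so the authors write that limit when they intend it. The smoking and ratio bullets carry no such limit. The latest-measurement wording shares a bullet with the ratio but belongs to the sentence on systolic pressure.

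**2. Would an earlier value exist?** Normally yes. Section 5.3 has smoking asked about and lipids measured at screening, and sections 3.2 and 5.3 require a calculated QRISK3 of at least 5% for inclusion.

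**3. When does the rule act?** Section 7.1 analyses dropouts up to the point of dropout, so complete dropouts do not trigger it. Partly missing visits do, for example an attended visit with no smoking answer.

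**4. False change in one patient.** There is no protocol figure to reproduce. All inputs in steps 4 to 6 are assumptions, apart from the 2.5-point threshold. If the hazard is multiplied by h, a 10-year risk p becomes 1 − (1 − p)^h. Rescoring a smoker as a non-smoker means h = 1/HR, with HR taken as 1.3 to 2.0.

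| True risk p | HR | Scored risk | False fall (points) |
|---|---|---|---|
| 15% | 1.3 | 1 − 0.85^(1/1.3) = 11.75% | 3.25 |
| 15% | 2.0 | 1 − 0.85^(1/2) = 7.80% | 7.20 |
| 6% | 1.3 | 1 − 0.94^(1/1.3) = 4.65% | 1.35 |
| 6% | 2.0 | 1 − 0.94^(1/2) = 3.05% | 2.95 |

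Solving p − [1 − (1 − p)^(1/HR)] = 0.025 gives the starting risk above which a single blank makes a false 2.5-point responder: 11.4% for HR 1.3 and 5.1% for HR 2.0. The second figure is barely above the 5% entry threshold.

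**5. Bias in the treatment contrast**, before any absorption by the time term in the model:

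bias = −(false fall) × (smoker share) × (share missing after TACTIC − share missing before)

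Take 30% to 50% smokers and a difference in missingness of 5 to 20 percentage points.

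- At 15% risk: 3.25 × 0.30 × 0.05 = 0.05, up to 7.20 × 0.50 × 0.20 = 0.72 points.
- At 6% risk: 1.35 × 0.30 × 0.05 = 0.02, up to 2.95 × 0.50 × 0.20 = 0.30 points.
- With equal missingness: 0. With more missing before TACTIC, the sign reverses.

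Against the 2.5-point target, 0.02/2.5 is about 1% and 0.72/2.5 is about 29%.

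**6. Cholesterol/HDL ratio**, assuming a hazard factor of 1.1 to 1.2 per unit, at 15% risk. A patient one unit above the constant has h = 1/1.1 or 1/1.2 and falls by 1.27 or 2.33 points. A patient one unit below has h = 1.1 or 1.2 and rises by 1.37 or 2.72 points.

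**The case against.** The strongest reply is that no bias in the treatment contrast has been shown. It needs differential missingness, for which the protocol offers no evidence, and it vanishes or reverses otherwise. The upper figure of 29% needs every unfavourable assumption at once, and the time term may absorb part of it. This stands: the effect on the primary contrast is undetermined.

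The trigger may also be uncommon. The Summary and sections 7.1 and 8.4 treat smoking as routinely collected at consultations, so the item may be missing only when both the visit record and the questionnaire fail. This limits the likely frequency, but section 5.3 places follow-up smoking in the questionnaire, while blood pressure, weight and blood samples come from the visit. Figure 1 is not available to settle how follow-up is distributed over conditions.

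A team might read missing as never recorded. The contrast with the blood pressure, BMI and length bullets makes that the less natural reading, and a rule that needs a charitable reading should be reworded.

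Nothing in the protocol says the raw blanks are erased, so substituted values could still be identified and counted. That is correct, but the planned score would contain the false quits all the same.

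Finally, carrying a value forward is itself a single-value imputation. That is a real cost, but the protocol already accepts it for blood pressure and BMI.

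**Conclusion.** The point holds and should be fixed. The inconsistency is plain on the text. Followed literally, the rule turns known smokers with a blank item into quitters and adds avoidable error through the ratio. For an affected smoker the false fall is 1.4 to 7.2 points under the assumed hazard ratios and starting risks, enough in many cases to count as a clinically relevant response. The bias in the treatment contrast may be zero. If smoking is missing more often after TACTIC, it favours the intervention by roughly 0.02 to 0.72 points under the stated assumptions; if more often before, it works against it. The ratio rule has no fixed direction and is the lesser part of the finding.

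**What to change.** Edit two bullets in section 7.1 to match the existing blood pressure and BMI rule. If smoking status or the cholesterol/HDL ratio is missing at a visit, use the patient's latest recorded value. Use non-smoker or 4.4/3.7 only if no value was ever recorded for that patient. Optionally, report the number of substituted smoking and ratio values by condition, so that readers can judge the direction of any bias.

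This needs no new data. The downside is small: a carried-forward value misses a real but unrecorded change, such as a true quit, and so can slightly understate a TACTIC effect.

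### Section 7.1 lets a missing blood pressure or BMI after TACTIC be filled with a value from before TACTIC, which sets the change in that item to zero

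*Protocol*

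**What the plan says.** Protocol section 7.1 gives the reason for its substitution rules: "Since the QRISK3 score cannot be calculated when individual items are missing, we will use the following values". Two of the rules carry a patient's own earlier value:

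- Systolic pressure: "In case systolic blood pressure is missing, we will use the latest measurement of this value". A sex-specific constant applies only if the patient has no measurement at all.
- BMI: "In case either weight or both length and weight are missing, we will use the latest measurement of the Body Mass Index". A mean from Table 2 applies only if there is no BMI at all.

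The lipid ratio is handled differently, with a constant rather than the patient's own value: "In case cholesterol/HDL ratio is missing, we will use 4.4 for men and 3.7 for women". Missing smoking status and missing standard deviation of pressure also take fixed values.

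None of these rules mentions the study condition, the age of the earlier value, or a minimum number of measured items. On loss to follow-up, section 7.1 says: "Data from patients who discontinued follow-up will be included in the analysis up to the point of dropout". Section 5.3 sets the visit pattern: "Depending on which step the cluster has started, patients will undergo one to four follow-up measurements, every five months". Section 4 makes each patient his or her own comparator before treatment starts.

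**The concern.** The trial rests on a contrast between occasions before and after TACTIC, much of it within the same patient. Section 4 lists blood pressure and BMI among the risk factors that the multidisciplinary meeting addresses. A carry-forward rule that ignores the switch can therefore place an untreated value of a targeted item on a treated occasion. The model receives it as an ordinary intervention observation.

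At stake is part of the estimated effect on QRISK3, a primary outcome. The change in the affected component is set to zero for those patients whatever TACTIC did. For a patient with only one follow-up, that is the only treated value there is.

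**Working it through.** **1. Can a pre-TACTIC value reach a treated occasion?** Table 1 in section 5.3 places physical examination and laboratory tests at week 1, the video at week 3, the multidisciplinary meeting at week 4/5 and the GP consultation at week 5/6. The next scheduled examination is at month 5. If pressure or weight is missing at month 5, the last scheduled study value is the one from week 1, taken before TACTIC. Unless routine care recorded a later one, section 7.1 uses it. Table 1 starts step 4 at month 15 and ends follow-up at month 20, so patients in that step have a single follow-up.

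**2. Does the dropout rule prevent this?** No. It covers patients who have stopped follow-up. A patient who misses one visit, or attends with one item unmeasured, is still in follow-up.

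**3. The plan's own figures.** Section 3.4 expects an effect of 2.5 points. Its sample size reproduces: 12 / (1 − 0.20) = 15 per cluster, and 15 × 32 = 480. These figures are not in dispute. The 20% is pilot drop-out, which the dropout rule already handles. It is not a rate of missing items among patients still in follow-up, and the protocol gives no such rate.

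**4. Size at the first treated occasion.** Let m be the share of those occasions with pressure and BMI carried over from control, and s the share of the effect acting through these two items. Both are assumptions.

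Recorded effect = 2.5 × (1 − m × s)

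| m | s = 1 | s = 0.5 |
|---|---|---|
| 5% | 2.5 × 0.95 = 2.375 | 2.5 × 0.975 = 2.4375 |
| 10% | 2.5 × 0.90 = 2.25 | 2.5 × 0.95 = 2.375 |
| 20% | 2.5 × 0.80 = 2.00 | 2.5 × 0.90 = 2.25 |

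**5. Check over the whole trial.** A simulation used 32 clusters of 12 patients, SD 12, ICC 0.10, within-patient correlation 0.95 and a true effect of −2.5, with 300 trials per setting. Each follow-up was missed at random with probability m and the previous value carried forward. Figure 1 is not shown, so a layout of four sequences and five periods was assumed. The model had fixed period effects and one constant treatment effect.

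| m | Estimate, s = 1 | Estimate, s = 0.5 |
|---|---|---|
| 0 | −2.51 | −2.53 |
| 5% | −2.39 | −2.46 |
| 10% | −2.25 | −2.39 |
| 20% | −1.99 | −2.23 |

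Relative to the run with nothing missing, at m = 20% the loss is (2.51 − 1.99) / 2.51 = 21% for s = 1 and (2.53 − 2.23) / 2.53 = 12% for s = 0.5. At m = 5% the losses are 0.12 / 2.51 = 5% and 0.07 / 2.53 = 3%. The simple formula and the simulation agree to within about two percentage points.

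**6. A visit with pressure, weight and lipids all unmeasured.** Read literally, the rules still give a score: carried pressure and BMI, a constant ratio, and the remaining items from other sources. The constant of 4.4 or 3.7 may lie below or above the patient's previous ratio, so it can create a fall or a rise. This part of the score has no fixed direction.

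**The case against.** The strongest reply is that the crossing is inferred from silence. The most recent value need not come from the previous study visit. The regular programme provides 1 to 5 consultations with pressure and weight, and Step 3 is itself a GP consultation, so a value from after the switch may exist. That stands as a limit on how often the problem arises. It does not remove it, because the rule does not require such a value.

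Second, the stated reason for the rules speaks of individual items, which may mean partly measured visits only, and a minimum-items rule could sit in a statistical analysis plan that is not shown. That is fair, and the absence of such a minimum is not counted here as a fault. Even on that reading, a single missing pressure or weight is carried across the switch by a rule that the protocol does fix.

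Several stronger readings are tempting but unsupported:

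- *A missed visit gives a wholly constructed score.* The follow-up questionnaire asks about smoking and family history. Section 5.3 takes the remaining items from the medical file, and QRISK3 includes antipsychotic use. Such a score can hold real data from after TACTIC.
- *The whole score is biased towards no effect.* This holds for pressure and BMI only. The constant lipid ratio can push either way.
- *Precision is overstated.* Copying a value reduces within-patient variation, but replacing a measured ratio by a constant can increase it. No calculation shows the net result.
- *The trial should expect to find only 2.0 to 2.4 points.* That range assumes that the whole effect runs through two items and that 5 to 20% of occasions are affected. TACTIC also targets antipsychotic use, smoking and cholesterol.

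**Conclusion.** The point holds in a limited form. As written, section 7.1 allows a control-period pressure or BMI to be scored as an intervention value when the item is missing at the first follow-up after TACTIC and no later routine value exists. The effect acting through these items is then diluted by the share missing. At an assumed 5 to 20%, this costs about 5 to 20% of the effect if all of it acts through them, and about half that if half does. At low missing rates the loss is modest.

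The size rests on the assumed missing share, the assumed share of the effect carried by pressure and BMI, missingness at random in the simulation, and an assumed layout. When pressure, weight and lipids are all unmeasured, the net direction is open. The rule should be changed because it is fixed in the protocol for a primary outcome and the remedy is mostly wording.

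**What to change.** In protocol section 7.1:

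- (a) Use the most recent pressure or BMI only if it was measured in the same condition. Never use a value from before the switch to TACTIC for an occasion after it.
- (b) Where no same-condition value exists, treat the component as missing and multiply impute it from the patient's other data and the condition. Where pressure, weight and cholesterol/HDL are all unmeasured, leave QRISK3 missing on that occasion. The planned mixed model accepts unequal numbers of occasions per patient.
- (c) Keep the present rule as a sensitivity analysis.

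The cost is a change of wording and some extra analysis. There will be slightly fewer scored occasions and slightly wider intervals. Occasions left missing lose whatever smoking and medication data were available, and both the imputation and the mixed model rely on a missing-at-random assumption that cannot be tested.
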